2. OVERVIEW

In this Phase 0 trial referred to as the G1 Study, we will enroll a retained sample of N=20 Spanish -speaking Latino PdS participants meeting positive finger prick screening for prediabetes. This is one of the very few studies to examine CGM use in Latinos with diabetes. Participants will wear CGM for a target of 20 days while keeping daily video logs relaying experiences of CGM use and feedback and interpretations of contingencies between changes in variables that changes glucose levels. At post-assessment, video-recorded structured interviews between staff and participants will explore the benefits and barriers to CGM use in daily life during the wear period. We will use video clips from the daily video logs and from the structured interviews to form the basis of the short smartphone educational clips for our *¡Mi Control!* intervention. We will then use an AI software tool (Descript) to transcode the captured video clips into text to be edited. After the sample of video clips is reduced to capture production value, a final series will be generated. Aim 1 in Study 1 is to create ten 30-60 second health communication video clips of *¡Mi Control!* to be paired with app-based CGM feedback to hasten learning about glucose control within 20 days. We will then use a different AI software to convert all video clips into multiple languages other than English and Spanish while retaining the visual likeness of the original characters in the videos. This will offer a proof of concept that the workload of health communication production can be reduced using this method to increase the capacity for message dissemination in future work.

During the planning phase of the G1 study, [name], PI, and the study staff drafted the study protocols to ensure that the MOP accurately described how the study procedures would be performed. Before developing the MOP, the final protocol, Electronic Case Report Form (eCRF), informed consent documents, and administrative forms (e.g., screening and enrollment log, protocol deviation log, etc.) were finalized. The development of the G1 Study and

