After the application of the sensor, the study staff will reiterate to the participant that as mentioned during the ICF process, the participant will create daily videos using their smartphones. The study staff will explain that the participant will create a video after obtaining a “high glucose” alert, in which they will describe what foods they ingested before receiving the alarm and they will describe in what situation they were in in the moment that they obtain the alert. The study staff will explain in addition, the participant will receive a daily text with 2 questions that the participant will answer on a video at the end of the day at approximately 6:00 p.m. The study staff will clarify that the purpose of the daily videos is to record their entire experience with the Dexcom sensor throughout the CGM wear phase. The study staff will

explain that every day at 6pm they will also receive an email containing a link with instructions on how to record themselves, and a section link where they will upload their daily videos.

Video Upload Practice

An email will be sent automatically after the participant signs the ICF. The email will contain a RC link in which the participant will be able to upload a practice video during the visit.

After providing a clear explanation, the study staff and the participant will create a practice video in which the staff will explain to the participant the importance of the lighting for the video, and that the participant's face should be clearly seen. The staff will inform the participant to make their videos in silent places, to eliminate other noises on their video's audio.

The study staff will kindly ask the participant to check their email to ensure that they have received an email titled "Video Upload." If the participant cannot locate the email, the study staff will help locate the email either in the participant's email inbox or in the spam folder. If the study staff is unable to locate the email, the study staff will check the email address that the participant provided during their screening call. After checking the correct email address, the study staff will immediately contact the study's statistician, so that the participant can receive the video upload link.

Compensation

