Semi-structured in-depth interview. The interview will take place in the PI's office. The interviewer will explain to the participants that the main purpose of the interview is to capture a narrative of their personal experience with the CGM transmitter, about how their experience with the CGM sensor changed their normal behavior towards their daily diets and physical activity. The interviewer will make the remark that we are not expecting specific answers, and that we want them to give us unmasked feedback from their experience within the study. The way the interviews will be structured is described on

pages 14 and 15. The research staff will use the Zoom app to record the interviews. The interviews will be recorded on the Zoom-Outlook cloud. Before the study staff starts recording the interview on the Zoom meeting, the study staff will make sure the participant fits perfectly in the camera frame, the only thing that can be shown in the background is the green screen behind the participant, the office's door must be completely shut, and all smartphones should be placed on "mute." The interview will last approximately 30 minutes.

An example of the Post-Visit Interview questions is provided in the Appendix I.

Anthropometric measures. The research staff will take height and weight measurements from each participant after they have completed each RC survey and have taken the Ravens task. These measurements will be taken at workstation 302-10 located in front of the PI's office where the scale/stadiometer will be placed. The measurements collected will be captured on a hard copy RC Body Measurements form.

Raven's Matrices Task

The study staff will create a Raven's Assessment for the participant and will utilize the following instructions:

The following steps apply to creating a single examinee/individual and administering the assessment one-on-one in person. These steps were created for the G1 study.

The study staff will add new participants to Q-Global:

-Select "New Examinee."

Fill in the following text boxes:

-First name: First Initial of first name

-Last name: First Initial of last name

-ID: REDCap ID

-Email

-Gender

-Birthdate

-Save

The study staff will assign Raven's 2 assessment to the new participant/examinee:

- Click on the checkbox associated with the participant
- Select "Assign Assessment."
- Click on "Assign New Assessment."
- Type "Raven" in the text box
- Select "Raven's 2 Digital LONG form

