### 2.1. Sample size calculation

This was a single-arm pre-post study. Consistent with recommendations for pilot studies, a sample size of 20 participants was chosen to assess feasibility and estimate outcome variability (i.e., to characterize typical ranges and within-person variability and to assess data completeness/quality) rather than to formally test hypotheses. With limited prior data for this exact population and protocol, the most informative use of the pilot sample was to obtain preliminary estimates (means, SDs, and within-person variability) with enough data density

per participant to support planning. Sample size considerations were also informed by principles of data saturation commonly applied in qualitative research. These pilot-derived variance components were then intended to inform a powered sample size calculation for the subsequent study designed to test intervention effects on CGM outcomes.

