#### **6.2. Other pre-specified outcome**

Videos obtained from informal and semi-structured interviews (total minutes).

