## 7. Analytic Dataset

Primary analyses will include participants with sufficient CGM data; inclusion required at least 2 days of valid CGM data within each 10-day assessment period. Descriptive analyses for other pre-specified outcome will include all participants that provided at least 1 video.

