### 8.3. Other pre-specified outcome

Descriptive statistics will be used to summarize the total minutes of videos captured and processed. For each participant, the total duration of videos will be calculated, and the following summary measures will be reported: number of participants with video data and mean  $\pm$  SD or median [IQR] total minutes of videos captured and processed.

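### The video-minutes summary leaves out participants with no video and does not split the total by source, so its mean can be overstated and it cannot show whether daily logging was feasible

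*SAP*

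**What the plan says.** SAP 7 fixes the analysis set: "Descriptive analyses for other pre-specified outcome will include all participants that provided at least 1 video". SAP 6.2 names the outcome as "Videos obtained from informal and semi-structured interviews (total minutes", and neither document defines 'informal'. In SAP 8.3, "For each participant, the total duration of videos will be calculated". The report then gives the "number of participants with video data and mean" with SD, or else the median with IQR. It plans no split by source, no count of videos and no count of days with a video.

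Protocol 3.13.2 describes three kinds of recording:
- **Interview.** Staff conduct and record it at the post visit: "The interview will last approximately 30 minutes".
- **Self-recorded videos during sensor wear.** On each day "the participant will receive a daily text with 2 questions that the participant will answer on a video at the end of the day". Further videos follow high-glucose alerts. No clip length is given.
- **Practice video.** It is uploaded with staff help at the baseline visit. Neither document says whether it counts as a video.

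On numbers, Protocol 2 says "we will enroll a retained sample of N=20", and SAP 2.1 says "a sample size of 20 participants was chosen to assess feasibility and estimate outcome variability".

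**The concern.** Two features make the summary hard to interpret.

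First, entry to the analysis set depends on a positive value of the outcome. Zero minutes is a legitimate result, and in a feasibility pilot an informative one, yet a participant with zero is left out of the mean or median.

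Second, a single total mixes recordings that ask very different things of the participant. The interview requires attending one visit that staff run. The daily videos require the participant to record and upload alone, day after day. If both go into the same total, someone who never recorded a daily video but came to the post visit passes the inclusion rule and contributes about half an hour.

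This matters because it is the only outcome listed under SAP 6.2, and Protocol 2 names the daily logs and the interviews as the two sources for the Aim 1 clips. A team planning the next study would want to know what each source yielded and how many people kept up the daily task.

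**Working it through.** The plan states no calculated figure for this outcome, so there is none to reproduce. The checks are simple arithmetic.

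**Inputs from the documents.** N = 20 (Protocol 2; SAP 2.1). Interview of about 30 minutes, and 20 wear days (Protocol 3.13.2).

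**Assumptions.** k is the number of participants with no video. m is the minutes per daily video, taken as 0.5 to 3 because no length is given. u is the fraction of days with a daily video. Alert-triggered videos are left out.

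**Step 1: denominator.** The mean over those with a video, divided by the mean over all with zeros counted, is N/(N−k).

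| k of 20 | 20/(20−k) | Excess |
|---|---|---|
| 0 | 1.00 | 0% |
| 1 | 1.053 | 5.3% |
| 2 | 1.111 | 11.1% |
| 4 | 1.25 | 25% |
| 5 | 1.333 | 33.3% |

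Anyone who completes the interview already has one video. If all 20 attend the post visit, k = 0 and there is no excess. The filter bites only on someone who leaves before the post visit without having uploaded anything, and not even then if the practice upload counts.

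**Step 2: recovery from SAP 8.3.** Given the number with video data, n, the all-participant mean is the reported mean × n/N. No such step recovers the all-participant median from a reported median and IQR.

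**Step 3: pooling, if 'informal' means the daily logs.** The interview's share of a participant's total is 30/(30 + 20um).

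| m (minutes) | Full-use total | Share at u = 1 | Share at u = 0.5 |
|---|---|---|---|
| 0.5 | 40 | 75% | 86% |
| 1 | 50 | 60% | 75% |
| 2 | 70 | 43% | 60% |
| 3 | 90 | 33% | 50% |

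A completer with no daily videos scores 30 minutes whatever m is. The u = 1 column is therefore also that person's score as a percentage of the full-use total.

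**Step 4: both effects in one invented example.** Suppose 2 participants have no video, 6 have the interview only, and 12 have the interview and all 20 daily videos, with m = 1.
- Total minutes: 12 × 50 + 6 × 30 = 780.
- Mean under the SAP: 780/18 = 43.3.
- Mean over all 20: 780/20 = 39.0, which is also 43.3 × 18/20.
- Daily-log part: 12 × 20/20 = 12.0. Interview part: 18 × 30/20 = 27.0.

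Over m = 0.5 to 3, the SAP mean runs from 36.7 to 70.0, the all-20 mean from 33.0 to 63.0, and the daily-log part from 6.0 to 36.0. In the example, 8 of 20 people made no daily video, and the planned output would not show it.

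**The case against.** The best defence is that this is a measure of content yield, not of adherence. The material feeds a small set of short clips drawn from both sources, so adding the sources together is coherent for that purpose. No test, sample size or decision depends on the figure. SAP 8.3 also reports how many participants had video data, so non-contributors are visible against the number enrolled. The distinction between sources survives in the study records: the editing log in Protocol Appendix V has separate columns for daily-video and interview transcripts, and Protocol 3.22 plans compliance summaries. All of this stands, and it keeps the severity low. It does not put a daily-logging result into the planned analysis. Because the interview counts as a video, the number with video data comes close to a count of post-visit attendance.

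Three stronger readings are tempting, and the documents do not support them:
- **That the mean is overstated.** The excess is zero if everyone has a video, and the interview makes the filter almost empty among completers. A sum over participants would not change at all.
- **That the SAP definitely pools the daily logs with the interview.** This is inferred from an undefined word. It is reasonable, because SAP 2 pairs daily narratives with the structured interview. On any other reading the daily videos have no pre-specified summary, which is also a gap.
- **That complete non-use of daily videos earns a fixed share of the maximum score.** The share moves from 33% to 75% with an assumed clip length, and alert-triggered videos mean that the full-use totals above are not a maximum.

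**Conclusion.** The point holds as a minor one. The analysis set depends on the outcome, so the mean can be overstated: by 0% if nobody lacks a video, and by 11% if 2 of 20 do. Those values of k are illustrations, since the documents give no expected number. The people affected would be mainly early leavers, and the reported count allows the mean to be corrected but not the median.

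The more lasting weakness is the missing split by source, which remains even with full retention. If 'informal' covers the daily logs, a completer with no daily videos still scores about 30 minutes. That is roughly a third to three quarters of a full-use total for clips of 3 to 0.5 minutes on 20 days, before alert-triggered videos. The total remains usable as a measure of how much material was collected. It cannot show whether daily logging was feasible, although feasibility is part of the stated reason for the sample size.

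**What to change.** - **SAP 7:** for this outcome, include all participants who had a sensor placed and count no video as 0 minutes.
- **SAP 6.2:** define 'informal', say whether alert-triggered videos belong to it, and exclude the baseline practice upload.
- **SAP 8.3:** report daily-log minutes, and days with a video out of each participant's own wear days, separately from interview minutes. Keep the total as a further line. A fixed denominator of 20 days would not suit everyone, because SAP 2 and Protocol 3.13 allow 14 to 20 wear days.

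The cost is SAP wording and a few more table lines. No new data collection is needed: participants enter the date with each upload, the interviews are recorded, and durations are already required for the planned total. The downside is a possibly lower headline figure.

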## 8. Statistical Analyses

### 8.1. Analytic oversight and preprocessing.

Descriptive statistics will summarize participant characteristics and outcomes (means  $\pm$  SD or medians [IQR]; proportions for categorical variables). Prior to modeling, distributions will be visualized to assess skewness/kurtosis; influential points will be evaluated (Cook's distance, DFBETAs) and addressed via winsorization or removal with justification. Outlier handling decisions will be documented a priori in the analysis plan. For CGM variable generation, raw 5-minute glucose values (excluding Day-1, replacement, and removal days to minimize calibration/transition artifacts) will be used for visualization (daily traces; AGP-style plots) and processed with the *iglu* R package to derive standardized metrics.

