### 8.2. Primary outcome.

For the primary outcome of mean glucose (mg/dL), we will first perform a Wilcoxon signed-rank test to compare paired mean glucose values between Phase A and Phase B, and then fit a linear mixed-effects model (LME) to estimate within-person change from Phase A to Phase B while accounting for repeated measures:  $Y_{ij} = \beta_0 + \beta_1(\text{Baseline}_i) + \beta_2(\text{Phase}_j) + \eta_i + \varepsilon_{ij}$  where  $\eta_i$  is a participant-level random intercept and Phase is categorical (A vs B). If assumptions are not met (e.g., skewed residuals), we will fit a linear quantile mixed model (LQMM) as a robust alternative. Candidate covariates (pre-specified) include baseline age, sex, and BMI. Note that additional exploratory analyses may be conducted to examine other demographic variables and baseline characteristics as covariates by assessing their potential associations with CGM outcomes. Variance inflation factors will be examined to rule out multicollinearity. Results will be reported as model-based estimates, corresponding 95% confidence limits, and p-value of the corresponding hypothesis test. All analyses will be performed in R ( $\geq 4.5.1$ ).

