## 9. Missing Data

Missingness will be characterized (MCAR/MAR) and addressed using likelihood-based methods and, if needed, multiple imputation or inverse probability weighting; sensitivity analyses will compare approaches.

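### SAP 8.1 allows influential points to be winsorized or removed without the rules it promises and requires no untrimmed result, so the variance meant to size the next study can come out too low

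*SAP*

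**What the plan says.** SAP 8.1 plans descriptive summaries and then, before modeling, an influence check by Cook's distance and DFBETAs. Influential points are to be "addressed via winsorization or removal with justification". It adds: "Outlier handling decisions will be documented a priori in the analysis plan". Separately, it drops some CGM data on technical grounds, "excluding Day-1, replacement, and removal days to minimize calibration/transition artifacts".

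SAP 8.2 gives the primary analysis: "we will first perform a Wilcoxon signed-rank test to compare paired mean glucose values between Phase A and Phase B", followed by a linear mixed model with a Baseline term, a Phase term and a participant random intercept. A linear quantile mixed model is the fallback if assumptions fail. On reporting: "Results will be reported as model-based estimates, corresponding 95% confidence limits, and p-value of the corresponding hypothesis test".

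SAP 2.1 says that n=20 was chosen to assess feasibility and estimate variability, "rather than to formally test hypotheses". On use of the output: "These pilot-derived variance components were then intended to inform a powered sample size calculation". The only sensitivity analyses in the SAP are in section 9 ("sensitivity analyses will compare approaches"), and they concern missing data.

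**The concern.** The advance documentation promised in 8.1 is not in the SAP. Four things are open: the cut-off for either diagnostic, the winsorizing percentile, the unit acted on (participant or phase row), and when to winsorize rather than delete. Both diagnostics also need a fitted model, so doing this before modeling leaves unclear which model supplies them. The SAP does not say whether the Wilcoxon test uses trimmed data, or whether the planning variances are taken before or after trimming.

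Influence on an estimate is not evidence of bad data. In a sample of 20 the most extreme valid participant is often influential, and acting on such points removes real between-person or within-person variation. The loss goes in one direction, and it falls on the quantity that section 2.1 wants from the pilot. The p-value reported under 8.2 can also become too small. That is secondary, because section 2.1 disclaims formal testing.

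**Working it through.** **Inputs from the SAP:** n=20 (2.1); Cook's distance and DFBETAs, winsorize or remove (8.1); Wilcoxon test, then mixed model (8.2). N=20 rests on pilot convention and data saturation, with no alpha, power, effect or SD, so there is no stated calculation to reproduce.

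**Assumed, because the SAP gives nothing:** the cut-offs, action on every flagged point, and the data shapes.

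**1. What a cut-off means at n=20.** For one paired change per participant and a mean-only model, h = 1/n and D = (e²/s²) × h/(1−h)², where e is the deviation from the mean and s the sample SD.
- D > 4/n: e²/s² > 0.2 × 0.9025/0.05 = 3.61, so |e| > 1.90 s. Any participant more than 1.9 SD from the mean is flagged.
- D > 1: e²/s² cannot exceed (n−1)²/n = 18.05, so D cannot exceed 18.05 × 0.05/0.9025 = 1.00. The rule never acts.

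**2. Clean data, no true change.** 40,000 samples of 20 normal changes, without Baseline or covariates. The variance ratio is mean trimmed over mean untrimmed variance.

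| Rule | Type I error, paired t / Wilcoxon | Variance ratio | Samples with a flag |
|---|---|---|---|
| None | 5.1% / 4.9% | 1 | – |
| Delete D > 1 | 5.1% / 4.9% | 1.000 | 0 |
| Winsorize 5/95% | 7.4% / 6.0% | 0.835 | – |
| Delete D > 4/n | 10.8% / 9.6% | 0.775 | 76% |
| Delete abs(DFBETAS) > 2/√n | 12.4% / 10.8% | 0.717 | 89% |
| Winsorize 10/90% | 11.0% / 8.6% | 0.685 | – |

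A separate run of 20,000 samples gave 0.771 for D > 4/n, and 0.824 for 5% winsorizing when values were clipped at the second lowest and second highest. With D > 4/n the ratio fell to 0.61 for t data with 5 df and 0.50 for lognormal data.

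**3. Clean data, mixed model on 40 rows with row deletion.** 2,000 datasets per intraclass correlation of 0.5/0.7/0.9; Monte Carlo error about 0.5-0.8 points. The SAP does not define Baseline, so it was taken as a participant-level covariate correlated 0.6 with the true level.
- Untrimmed: type I error 5.2/5.2/4.8%; D > 1 the same.
- D > 4/20: 6.2/6.0/5.2%, residual variance ratio 0.959/0.972/0.991.
- D > 4/40: 10.7/11.2/9.3%, ratio 0.775/0.795/0.847, at least one row flagged in 86/76/53%.
- D > 4/40 without Baseline: 13.9/13.6/11.8%, ratio 0.701/0.695/0.707.

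This part was simulated once; the paired-change variance ratios and t-test error rates were repeated and agreed.

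**4. One wrong value.** If one of 20 changes carries an error of δ SD, the expected untrimmed variance is 1 + δ²/n: 1 + 9/20 = 1.45 for 3 SD and 1 + 25/20 = 2.25 for 5 SD. Simulation (15,000 runs) gave 1.453 and 2.253. D > 4/n gave 0.910 and 0.965; winsorizing 5/95% gave 1.024 and 1.069.

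**5. Effect on the next study.** Assume that its N is proportional to this variance and is set for 80% power. True power is Φ((1.960 + 0.842) × √ratio − 1.960).
- 0.835: Φ(2.802 × 0.914 − 1.960) = Φ(0.600) = 72.6%
- 0.775: Φ(0.507) = 69.4%
- 0.685: Φ(0.359) = 64.0%
- 0.847: Φ(0.619) = 73.2%
- 0.959 and 0.991 (rows, D > 4/20): about 78% and 80%

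In case 4 the same assumption makes a study sized on untrimmed data 1.45 or 2.25 times too large.

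**The case against.** The missing rule and the missing untrimmed result are hard to dispute. The consequence is more open.

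- *The descriptive SDs in 8.1 come before the influence check and may be untrimmed.* Possible, but the SAP does not say so, and variance components would naturally come from the model fitted after the check.
- *The cut-offs are assumed, and action needs justification.* True. A D > 1 rule does nothing, and D > 4/20 in the mixed model with Baseline costs only 1-4% of the residual variance. That range is the size of the choice left open. A justification written after influence has been seen is not the advance rule that 8.1 promises.
- *At n=20 the SD is imprecise anyway.* Under normality its 95% limits are about 0.76 to 1.46 times the estimate. That error runs both ways; trimming valid data adds one that runs down only.
- *Trimming protects against bad data.* It does: with one gross error, 5/95% winsorizing recovers the variance well and untrimmed data overstate it badly. Protocol 3.17.3 has a CGM error form that records when each error began and was resolved, but a sensor sending plausible wrong values may never trigger it. The sample form in Appendix R labels only start and stop dates, without times. Section 7 of the SAP accepts 2 valid days per period, so one bad day can carry a phase mean.

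The last point stands in part. It is the reason to show trimmed values beside the untrimmed ones.

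**Conclusion.** The concern holds. SAP 8.1 permits data-dependent trimming, promises advance rules that the SAP does not contain, and has no untrimmed analysis as a safeguard.

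For clean normal data and automatic action, the planning variance is unchanged with D > 1, 16-17% low with 5/95% winsorizing, 22-23% low with D > 4/n and 31-32% low with 10/90% winsorizing. For the mixed model with Baseline it is 1-4% low (D > 4/20) or 15-23% low (D > 4/40). Power in a next study sized at 80% falls to about 73% with 5/95% winsorizing, 69% with D > 4/n, and 69-73% with D > 4/40 on rows. These sizes rest on assumed cut-offs, action on every flag, an assumed Baseline covariate and N proportional to the variance. Justified, selective action would do less; heavier tails would do more. The change should be made, but it does not invalidate the study.

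**What to change.** In SAP 8.1 and 8.2, state that the Wilcoxon and mixed-model analyses use every participant in the analysis set, without winsorization or deletion. The only exception is readings invalid for a documented device fault, decided from the CGM error form and not from influence. Complete the form with times as well as dates, as Protocol 3.17.3 describes, so that readings can be matched to faults.

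Add one trimmed sensitivity analysis with a single stated cut-off or percentile, unit and action. Name the model that supplies any influence diagnostic.

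In SAP 2.1, state that SDs and variance components for planning come from the untrimmed data after documented-fault exclusions, and print the trimmed values next to them. A large gap between the two then warns of an undocumented error before the next study is sized.

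The cost is SAP wording and one extra analysis. The downside is a wider interval and a larger planning SD if one participant is extreme or carries an undocumented error: up to 2.25 times the variance in the 5 SD example.
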